1.2 Secondary Outcomes

To evaluate global, individual, and economic effects of our multi-condition strategy, we will report a number of secondary outcomes *for each study arm at 12, 24 and 36 months*:

- 1) measures of "common effect," i.e., whether the intervention had a similar beneficial effect on all four main targets (SCL-20, HbA1c, SBP, LDL-c);¹
- 2) proportion of participants achieving all 3 CVD risk factor targets in the two groups;
- 3) mean reductions in four main targets (SCL-20 score; HbA1c; SBP; LDL-c);
- 4) proportion of participants achieving treatment targets or significant reductions in individual outcomes (reduced depressive symptoms [$\geq 50\%$ reduction in SCL-20], glycemic control [HbA1c $\leq 7.0\%$ or $\geq 0.5\%$ reduction], BP control [SBP ≤ 130 mmHg or ≥ 5 mmHg reduction], lipid control [LDL ≤ 100 mg/dl or ≥ 10 mg/dl reduction]);
- 5) mean utility, quality of life, and participant treatment satisfaction scores; and
- 6) mean health expenditures and within-trial cost-utility.

2 Background

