10.1 Primary and Secondary Health Outcomes

Participants in both arms will be invited for 6-monthly assessments [0, 6, 12, 18, 24 and 36 month time-points] for blinded outcomes assessors. Data for health outcomes analyses will include demographic (age, sex, marital status, education, occupation, income, migration status), anthropometric data (height, weight, waist circumference), depression (SCL-20 and PHQ-9), and risk factor levels (fasting blood glucose, HbA1c, BP, lipid levels, and tobacco use). Data regarding patient-centered outcomes such as treatment satisfaction, quality of life and utility [reflects participants' judgments regarding different health states on a continuum from 0.0 (representing death) to 1.0 (perfect health)] will be collected using the Summary of Diabetes Self Care Activities, Diabetes Treatment Satisfaction Questionnaire, and Health Utilities Index-3.

Data Analysis: Recruitment and retention of trial participants will be assessed by examining: number screened, number eligible to be randomized, number enrolling in the study, and dropout from regular testing at the completion of 36 months. We will test for differences in baseline characteristics to assess randomization using appropriate statistical tests for sample proportions [χ^2] or means [t-tests]. Between-group differences in primary and secondary outcomes will be assessed at 12, 24 and 36 months, using the following indicators:

- **Primary Outcome:** At each time-point, we will test the unadjusted difference in the proportion achieving the primary outcome, which jointly evaluates depressive symptoms and CVD risk reduction.

- Secondary Outcomes:** Given the objective of assessing the cumulative benefits of a multi-component intervention, a “common treatment effect” will be tested on all four main targets [SCL-20, HbA1c, SBP, LDL-c] jointly using a scaled marginal model.¹ Each target, measured continuously, is scaled by its standard deviation and a single parameter is estimated representing the “common effect” on all targets. The advantage of this approach is that all targets can be measured continuously, thereby improving power, and a “common effect” in standard deviation units is produced. Katon¹⁸ used this approach in a similarly designed trial [the model is estimable using the SAS PROC GENMOD procedure²⁶ described by Roy].¹

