- Additional secondary outcomes that will be evaluated include: (1) a measure of “common effect,” i.e. whether the intervention had a similar beneficial effect on all four main targets [SCL-20, HbA1c, SBP, LDL-c];¹ proportion of participants achieving all 3 CVD risk factor targets; (2) mean reductions in four main targets [SCL-20 score; HbA1c; SBP; LDL-c]; (3) proportion of participants achieving treatment targets or significant reductions in individual risk factors (depression control [$\geq 50\%$ reduction in SCL-20]; glycemic control [HbA1c $\leq 7.0\%$ **or** $\geq 0.5\%$ reduction]; BP control [SBP ≤ 130 mmHg **or** ≥ 5 mmHg reduction]; lipid control [LDL ≤ 100 mg/dl **or** ≥ 10 mg/dl reduction]; (4) mean utility, quality of life, and depression- and diabetes-specific patient satisfaction scores; and (5) mean health expenditures and within-trial cost-utility.

All analyses will be conducted with both intention to treat (ITT) and per protocol analytical approaches. All treatment effects (primary and secondary outcomes) will be assessed using multivariate regression models adjusted for baseline characteristics. Generalized linear models will be estimated with appropriate link functions and error distributions for each outcome [e.g., logit models for dichotomous outcomes]. Heterogeneity in treatment effects across sites will be tested with interaction terms between site and the treatment variable. Similarly, heterogeneity in treatment effect by baseline age, gender, socioeconomic status, SCL-20, HbA1c, SBP, and LDL-c will also be evaluated. Robust standard errors will be estimated to account for within-site clustering [design effects].

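### The common-effect outcome is defined as similarity of benefit across the four targets, but its one-parameter model assumes similarity and can only measure average benefit

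*Combined protocol and SAP*

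**What the plan says.** The common effect is the first item in the secondary-outcome list in section 1.2, to be reported at 12, 24 and 36 months. It is explained there as "whether the intervention had a similar beneficial effect on all four main targets (SCL-20, HbA1c, SBP, LDL-c"). The list of additional secondary outcomes in section 10.1 repeats the explanation: "whether the intervention had a similar beneficial effect on all four main targets [SCL-20, HbA1c, SBP, LDL-c"].

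The method is in the secondary-outcomes paragraph of section 10.1. The four targets are tested "jointly using a scaled marginal model". Each continuous target "is scaled by its standard deviation and a single parameter is estimated representing the" common effect, expressed in SD units. That paragraph opens with a different purpose: "Given the objective of assessing the cumulative benefits of a multi-component intervention".

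Two other parts of section 10.1 bear on the point. The targets are also to be analysed one at a time, including "mean reductions in four main targets [SCL-20 score; HbA1c; SBP; LDL-c"] and the proportion reaching target or a significant reduction on each. On heterogeneity, "Heterogeneity in treatment effects across sites will be tested with interaction terms between site and the treatment variable", and a similar evaluation is planned by baseline age, gender, socioeconomic status, SCL-20, HbA1c, SBP and LDL-c. In that list the four targets are baseline moderators, not outcomes to be compared with one another.

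**The concern.** A model with one treatment parameter for four scaled outcomes imposes equality of the four scaled effects and estimates their average. It has no term that could show a difference between targets. A significant result says that the average effect in SD units is not zero. It does not say that the effects are alike, which is how sections 1.2 and 10.1 define the outcome.

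What is at stake is the interpretation of a listed secondary outcome in an integrated-care trial. A common effect driven mainly by depressive symptoms would carry a label that, by the plan's own definition, means similar benefit on glucose, blood pressure and lipids as well. Nothing else in the plan tests the claim in that label.

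**Working it through.** The documents give no power, effect size or correlation for this analysis, so there is no stated figure to reproduce. The only sample size they derive is for the primary outcome (section 4.1). With 15% versus 30%, 80% power, a continuity correction and an assumed two-sided alpha of 0.05, the calculation gives 134 per arm, or 268 in total, and 268/0.80 = 335. Both match the plan.

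**Inputs for the illustration**
- Evaluable per arm: section 4.1 aims for 360 participants in equal arms and allows 20% loss, so n = 360 × 0.80 / 2 = 144.
- Assumed: unit SD for each scaled target, a common between-target correlation ρ of 0.1 or 0.3, and a two-sided 5% level.
- Assumed effects in SD units, both with mean 0.15: unequal (0.6, 0, 0, 0) and equal (0.15, 0.15, 0.15, 0.15).

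**One-parameter model**

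The estimate is taken as the equal-weight average of the four scaled differences (working independence).
- Estimate: 0.6/4 = 0.15 for the unequal pattern and 0.15 for the equal one.
- SE = √[(2/n)(1 + 3ρ)/4]. For ρ = 0.1: √(0.013889 × 1.3/4) = 0.0672, z = 0.15/0.0672 = 2.23, power 60.7%. For ρ = 0.3: √(0.013889 × 1.9/4) = 0.0812, z = 1.85, power 45.5%.

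Neither the estimate nor its SE depends on how the effect is spread over the targets, so the two patterns give the same result.

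**Four-parameter model with a 3-df test of equality**

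The non-centrality is Σ(dⱼ − d̄)² / [(2/n)(1 − ρ)], where dⱼ is the scaled effect on target j and d̄ is the mean of the four. For (0.6, 0, 0, 0) the sum of squares is 0.45² + 3 × 0.15² = 0.27.

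| Pattern (SD) | Sum of squares | Rejects, ρ = 0.1 | Rejects, ρ = 0.3 |
|---|---|---|---|
| 0.15 on all four | 0 | 5% | 5% |
| 0.6, 0, 0, 0 | 0.27 | 98.3% | 99.7% |
| 0.3, 0.3, 0, 0 | 0.09 | 60% | 72% |
| 0.3, 0.1, 0.1, 0.1 | 0.03 | 22% | 28% |

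At ρ = 0.1 the non-centralities of the last three rows are 21.6, 7.2 and 2.4.

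**Simulation check**

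With 134 per arm, 4,000 replicates per scenario and correlations 0, 0.2 and 0.4, four patterns with mean 0.20 SD were compared: equal effects; (0.8, 0, 0, 0); (0.5, 0.3, 0, 0); and (0.6, 0.6, −0.2, −0.2), in which two targets worsen. The one-parameter estimate was 0.198 to 0.202 throughout. Its rejection rate was about 90%, 74% and 58–60% at the three correlations, whatever the pattern. The equality test rejected in about 6% under equal effects, 86–98% for (0.5, 0.3, 0, 0), and 99.9–100% for the other two.

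**The case against.** The strongest reply is that the model is right and only the gloss is loose. Section 10.1 introduces it to assess cumulative benefit, and a single SD-scaled parameter is a reasonable joint test for that. This stands: the model should stay. It does not remove the mismatch, because both lists of secondary outcomes define the result as similarity.

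A reader might go further and infer that a depression-only effect would be reported as similar benefit on all four targets, so that the trial would publish a wrong answer. The documents do not support that. They set no such reporting rule, and they require results for each target. With effects of (0.6, 0, 0, 0) SD and 144 per arm, the SCL-20 comparison alone has z = 0.6/√(2/144) = 5.09 and is significant about 99.9% of the time, while each other target is significant about 5% of the time. The planned report would show the pattern. What it would lack is a common scale and any formal comparison across targets.

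A second tempting step is to allow a claim of similarity whenever equality is not rejected and all four estimates favour the intervention. That rule is unsound. At ρ = 0.1 it would allow the claim about 48% of the time for (0.3, 0.1, 0.1, 0.1) SD, and deny it about 34% of the time when all four effects truly equal 0.15 SD.

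Finally, section 10.1 refers to outside sources for the fitting of the model. Whether those include a check of the common-effect assumption cannot be seen from the documents, and the plan itself states none.

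**Conclusion.** The point holds as a mismatch between the definition of a secondary outcome and its analysis. The one-parameter result can support a statement about average standardised benefit. It carries no information on whether the benefit is similar across targets, and the planned heterogeneity analyses, by site and by baseline factors, do not supply it.

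This conclusion follows from the structure of the model and does not depend on the assumed effects, correlations or sample size. The figures only illustrate it: the same 0.15 SD and the same power (61% at ρ = 0.1, 46% at ρ = 0.3) for a one-target effect and a uniform one.

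The consequence is limited. It touches one secondary outcome, the analyses of each target soften it, and the primary outcome, its test and the sample size are unaffected. The change is worth making because it costs little and the label otherwise promises more than the model can show.

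**What to change.** 1. In sections 1.2 and 10.1, redefine the one-parameter result as the average standardised effect across the four targets, described as a joint test of overall benefit.
2. From the same scaled marginal model, fit four target-specific scaled effects and report each with a 95% CI, so that all four can be read on one scale.
3. Add the 3-df Wald test of equality as a check on the common-effect assumption, shown next to the one-parameter estimate.
4. State that non-rejection is not evidence of similarity, and that any statement about similarity rests on the four estimates and their CIs.

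The cost is a wording change and one extra model fit, with no new data. The drawback is the test's low power for moderate differences (the 22% and 28% in the last row of the table), which is why the CIs must carry the interpretation.

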1.1.1 Hypothesis

Compared to the control group, a higher proportion of intervention participants (30% vs. 15%) will achieve combined improvements in depressive symptoms and CVD risk factor levels ($\geq 50\%$ reduction in SCL-20 score AND one or more of the following: $\geq 0.5\%$ reduction in HbA1c, ≥ 5 mmHg reduction in SBP, or ≥ 10 mg/dl reduction in LDL-c) at 24 months.

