4.1 Sample Size

The study is powered on between-arm differences in the proportion achieving the primary outcome [*combined depression and CVD risk factor improvements* ($\geq 50\%$ reduction in SCL-20 **and** ≥ 1 of: $\geq 0.5\%$ reduction in HbA1c **or** $\geq 5\text{mmHg}$ reduction in SBP **or** $\geq 10\text{mg/dl}$ reduction in LDL-c)] at 24 months post-randomization. The sample size estimation is guided by: (1) studies in India^{14,15} and elsewhere^{16,17} showing that $<50\%$ of all people with diagnosed diabetes routinely achieve single or multiple CVD risk factor targets; and (2) published results by Katon¹⁸ demonstrating a 30% between-group absolute difference [60% (TEAMCare) vs. 30% (usual care)] in proportions of subjects achieving $\geq 50\%$ reduction in SCL-20 score at 12 months and 15% absolute difference [37% vs. 22%] in the proportion of subjects achieving significant reductions or target control for all three CVD risk factors [HbA1c, SBP, LDL-c]. It is anticipated that a 15% absolute difference [30% of intervention arm participants will achieve combined and sustained reductions in depressive symptoms **plus** ≥ 1 CVD risk factor at 24-months post-randomization, compared to 15% of usual care participants]. Using a two-sample test of equality of proportions and a normal approximation with a continuity correction in Stata Version 12.0., we calculated that $n=268$ provides 80% power, and $n=335$ allows additional 20% for loss to follow-up. The aim is to recruit an enhanced sample of 360 participants, assigned equally to the two arms with the goal of randomizing 120 participants across the four clinic sites.

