8	Follow-up visit with diabetes physician – If depressive symptoms or poor control persists , more intensive psychotherapies or doses.	Review of behavioral activation progress. Continued motivational enhancement and behavioral activation (guided activity).	Scheduled follow-up CC telephone calls.
10-16	As needed follow-up visits with CC (in-person or phone): review of control and adherence.	Review of behavioral activation progress. Continued motivation; behavioral activation.	
25-52	Monthly tailored follow-up (in-person or phone): support maintenance / relapse prevention.	Individual booster behavioral activation sessions.	

Each intervention participant will be enrolled in the integrated depression and diabetes care program (proactive follow-up and case reviews) for 12 months. All participants (intervention and control) will undergo outcomes assessments for months 0-36 (visits at 0, 6, 12, 18, 24 and 36 months following randomization). The focus of the 13-36 month assessments is to evaluate if effects of the intervention are sustained.

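### The plan gives no method for missing 24-month outcomes: the ITT analysis is complete-case by default, and the 6-, 12- and 18-month values do not inform the 24-month effect

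*Combined protocol and SAP*

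**What the plan says.** Section 10.1 assesses outcomes at 12, 24 and 36 months. The primary composite is tested at each time point as a crude difference between the two proportions. Treatment effects are also estimated by regression adjusted for baseline characteristics: "Generalized linear models will be estimated with appropriate link functions and error distributions for each outcome", with a logit model given as the example for binary outcomes. Robust standard errors are there for clustering by site, not for repeated measurements on one participant. The common-effect analysis is a joint scaled marginal model over the four continuous targets.

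On analysis sets the section says "All analyses will be conducted with both intention to treat (ITT) and per protocol analytical approaches". Neither set is defined.

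Loss to follow-up appears only in section 4.1, where the larger sample size "allows additional 20% for loss to follow-up". Section 5.2 schedules "visits at 0, 6, 12, 18, 24 and 36 months following randomization", and Table 4 shows SCL-20, HbA1c, blood pressure and lipids at all of them.

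The text contains no longitudinal model, imputation, weighting, rule for a missing outcome, or rule for a composite with some components missing. The only sensitivity analyses named are in section 10.2 and concern the economic model.

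**The concern.** A test of two proportions, or a logit model at 24 months, can use only participants whose 24-month composite is known. Without a further rule, everyone else drops out of the analysis. The estimate is then for completers, although it is labelled ITT.

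This biases the difference if dropout is related to response and the relation or the amount differs by arm. The protocol makes that plausible. The intervention arm has far more contact with study staff. Section 7.1.1 allows removal from the study over self-harm concern. Section 9.8 lists adverse events and clinical outcomes, not the four components, for annual follow-up of discontinued participants. Sections 5.2 and 7, however, say that all participants are assessed or approached unless they withdraw, so it is unclear whether discontinued participants supply primary-outcome data.

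The composite adds a second gap. A known SCL-20 non-response settles it as a failure even with all laboratory values missing. An SCL-20 response plus one qualifying CVD improvement settles it as a success even with the other values missing. No rule says so, which leaves the decision open until after the data are seen.

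**Working it through.** **1. The plan's own figures.** Inputs: "a higher proportion of intervention participants (30% vs. 15%) will achieve combined improvements in depressive symptoms and CVD risk factor levels" (section 1.1.1), 80% power, and "Using a two-sample test of equality of proportions and a normal approximation with a continuity correction" (section 4.1). Alpha is not stated; two-sided 0.05 is assumed.

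- Uncorrected n per arm = [1.960·√(2·0.225·0.775) + 0.842·√(0.30·0.70 + 0.15·0.85)]² / 0.15² = 120.5.
- With continuity correction: (120.5/4)·[1 + √(1 + 4/(120.5·0.15))]² = 133.5, so 134 per arm and 268 in total.
- Loss allowance: 268/0.80 = 335. Both stated figures reproduce.

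**2. Power is not the problem.** Section 4.1 targets 360 and the objective says 400. A 20% loss leaves 288 or 320 participants, with continuity-corrected power of 83% or 87%.

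**3. Bias from dropout tied to earlier response.** Assumptions, none from the documents except 30% v 15%: the CVD part is met by 60% independently of SCL-20, so SCL-20 response is 50% v 25% (0.30/0.60 and 0.15/0.60) at both 18 and 24 months. The two visits are linked by latent normals with correlation 0.5 or 0.7. Dropout depends on 18-month response only.

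Complete-case rate = 0.60 × Σ(share × kept × P(24-month response)) / Σ(share × kept), summed over 18-month responders and non-responders.

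P(24-month response) for 18-month responders and non-responders:
- intervention: 0.667 and 0.333 (correlation 0.5); 0.747 and 0.253 (0.7)
- control: 0.481 and 0.173 (0.5); 0.602 and 0.133 (0.7)

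Worked case, intervention arm, correlation 0.5, losing 10% of responders and 30% of non-responders: 0.60 × (0.45·0.667 + 0.35·0.333)/0.80 = 31.25%. With control loss unrelated to response, the difference is 31.25 − 15.0 = 16.25 points.

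| Loss of 18-month responders / non-responders | Difference, correlation 0.5 | Correlation 0.7 |
|---|---|---|
| Intervention 10%/30%; control 20%/20% | 16.25 | 16.9 |
| Intervention 20%/20%; control 5%/25% | 14.1 | 13.7 |
| Intervention 10%/30%; control 30%/16.7% | 16.8 | 17.7 |
| Both arms 10%/30% | 15.3 | 15.4 |

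The truth is 15.0 in every row. Overall loss is 20% per arm, except control in the last row: 0.25·10% + 0.75·30% = 25%. Other assumed patterns have given 12.5 to 19.4. Weighting on 18-month response returns 15.0 in each row, but only because dropout was assumed to depend on nothing else.

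**4. Harsher mechanisms.**
- Dropouts respond at half the completer rate, 20% lost per arm: 0.30/0.90 − 0.15/0.90 = 16.7 points.
- Same halving, 30% v 10% lost: 0.30/0.85 − 0.15/0.95 = 19.5 points.
- Intervention arm only, losing 10% of responders and 30% of non-responders by their 24-month SCL-20 status: 0.60·0.50·0.90/0.80 − 0.15 = 18.75 points. Weighting on 18-month response still gives 17.8 to 18.3.
- Bounds if completers show 30% v 15% and 20% are missing per arm: 0.24 − 0.32 = −8 to 0.44 − 0.12 = +32 points.

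**5. Precision for the continuous targets.** With 20% missing, one earlier visit correlated ρ with the 24-month value and no baseline adjustment, the gain in effective sample size is 1.25/[ρ² + (1 − ρ²)/0.8] − 1:
- ρ = 0.6: 1.25/1.160, or 7.8%
- ρ = 0.7: 1.25/1.1275, or 10.9%

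If baseline is already in the model and correlations are exchangeable, replace ρ by ρ/(1 + ρ). The 18-month visit then adds about 3% to 3.5%, and all three earlier visits about 5% to 6%.

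**The case against.** The strongest reply is that the plan is silent rather than wrong. A reader might infer that it drops a fifth of the participants, fits a separate model at each visit and ignores the interim data. The documents do not support that:

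- Nothing excludes participants without 24-month data. Models are described by outcome; the time-point wording belongs to the crude test of proportions.
- The 20% is a planning allowance, not a forecast of missing 24-month outcomes.
- The 12-month data are analysed at their own time point, and 6-monthly utilities enter the QALY calculation in section 10.2.
- The common-effect analysis is already one joint model.

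All of this stands, and it limits the point to what happens by default.

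The size is also open to challenge. Bias needs dropout that is related to outcome after adjustment. A baseline-adjusted completer model is not biased if missingness depends only on arm and the included covariates. With 144 per arm the standard error is √(0.30·0.70/144 + 0.15·0.85/144) = 4.8 points, so the largest shift in the table, 2.7 points, is about 0.6 standard errors. Borrowing 18-month data also helps little if dropout depends on 24-month status. These points stand too. They argue for sensitivity analyses alongside imputation, not for leaving the handling unstated.

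A mixed model for the continuous targets is partly preference: baseline-adjusted regression at a fixed visit is acceptable where little is missing.

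**Conclusion.** The concern holds in limited form. Section 10.1 has no method for missing outcomes and no definition of ITT. Its stated analyses default to complete cases, and no stated method lets the earlier component values inform the 24-month effect.

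Under assumed patterns with about 20% loss per arm, a true 15-point difference appears as roughly 14 to 18 points when dropout is tied to 18-month response and differs by arm. It appears as 15.3 to 15.4 when the pattern is similar in both. The range moves with the assumed pattern.

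A reader might infer that the trial's result will be biased, or that imputation would remove any bias. Neither follows: the first needs differential, outcome-related dropout, and the second needs missing at random. The precision gain is a minor benefit. This is a cheap improvement worth making, not a fault that invalidates the design.

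**What to change.** Change the analysis section as follows:

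- **ITT:** all randomised participants, in the arm assigned.
- **24-month composite:** multiply impute SCL-20, HbA1c, SBP and LDL-c separately by arm, using baseline and all earlier visits. Derive the composite in each completed data set, then run the planned comparison and combine the results.
- **Scoring rule:** where observed components settle the composite, they decide it. A known SCL-20 non-response is a failure. An SCL-20 response with any one qualifying CVD improvement is a success.
- **Continuous targets:** one mixed model for repeated measures over the 6-, 12-, 18-, 24- and 36-month visits, with arm-by-visit, site and baseline value.
- **Sensitivity analyses:** missing equals failure, and delta-adjusted imputation with the shift varied by arm. With completers at 30% v 15% and 20% missing in each arm, missing equals failure gives 0.8·30% − 0.8·15% = 12 points.

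The cost is plan wording and modest programming; no new data are needed. The downside is that the main analysis relies on missing at random, which the delta-adjusted analysis is there to test. Participants lost early also have fewer visits to draw on.

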2.5 The INDEPENDENT Study

This study will develop and test an integrated depression and diabetes care model in four ambulatory diabetes clinics in India. Our evaluation plan will generate usable evidence regarding effectiveness, quality of life, and costs.²

The collaborative care intervention in this study will incorporate unique aspects of Indian culture gathered from focus group discussions and in-depth interviews with participants, family members, and health care providers at all clinic research sites. We will endeavor to make the intervention more participant-centered, develop locally-understandable educational materials for participants in India, and identify ways to overcome stigma of mental health disorders while facilitating trustful therapeutic relationships between nurse managers and the participants and their families.

Several additional benefits will emerge from this study, including: (a) identifying unrecognized depressive symptoms among several hundred diabetic patients and working with their regular providers to manage this appropriately; (b) training a cadre of care coordinators (CC) who can motivate better self-care for high-risk individuals; (c) offering a toolbox of therapeutic options (family-centered or other culturally-sensitive activation models such as spirituality, yoga, or meditation) in order to customize care according to the individual's preferences; and (d) developing software technology that prioritizes participants for review,

prompts treatment plan recommendations and modifications, and makes case review meetings efficient by providing an overview of key participant indicators in one place (the “dashboard”).

3 Study Design

The study is a four site, single-blind, individually randomized controlled implementation trial. Blinding outcome assessments and randomization will limit biases and evenly distribute participant characteristics.

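### Clustering the adjusted models' standard errors on only four sites gives about 14–21% false positives with a z reference, or about 50–57% power with t(3), and breaks the site-by-treatment test if it uses the same variance

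*Combined protocol and SAP*

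**What the plan says.** Section 3 (Study Design) describes the trial this way: "The study is a four site, single-blind, individually randomized controlled implementation trial".

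Section 10.1 has two layers of analysis. For the primary outcome at each time-point, "we will test the unadjusted difference in the proportion achieving the primary outcome". It then adds a second layer: "All treatment effects (primary and secondary outcomes) will be assessed using multivariate regression models adjusted for baseline characteristics". These are generalised linear models, with a logit link for binary outcomes. Two heterogeneity analyses follow: "Heterogeneity in treatment effects across sites will be tested with interaction terms between site and the treatment variable" and "Similarly, heterogeneity in treatment effect by baseline age, gender, socioeconomic status, SCL-20, HbA1c, SBP, and LDL-c will also be evaluated". The paragraph ends with the variance rule: "Robust standard errors will be estimated to account for within-site clustering [design effects".

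No small-sample correction, reference distribution or degrees of freedom is given, and the plan does not say whether site enters the models as a covariate. The sample size in Section 4.1 rests on "a two-sample test of equality of proportions and a normal approximation with a continuity correction", with no allowance for clustering.

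**The concern.** A cluster-robust (sandwich) variance is estimated from one summed score per cluster. With four sites there are four such sums, so the estimate is biased low and very noisy. It is trustworthy only when clusters are many.

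Nor does the design call for it. Individuals are randomised and both arms are present at every site, so differences in site level cancel out of the treatment comparison or are absorbed by site indicators. Clustering would matter for generalising to other sites when the treatment effect varies between sites, and four sites cannot support that with useful power.

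At stake are the adjusted estimate reported beside the primary result, the secondary outcomes analysed in the adjusted models, and the tests of whether the effect differs by site or baseline factor. The scaled marginal model (Section 10.1) and the cost-utility ratio (Section 10.2) do not mention site clustering, and nothing is claimed about them.

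**Working it through.** **Inputs from the documents.** Four sites and individual randomisation (Section 3). Rates of 30% vs 15% (Section 1.1.1). 80% power at 268, or 335 with 20% loss, and a target of 360 (Section 4.1). A target of 400 (Section 1). After 20% loss, 360 leaves 288 and 400 leaves 320.

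**Step 1: the plan's own figure.** Alpha is not stated, so two-sided 5% is tried. Per arm, before correction:

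n = [1.96·√(2·0.225·0.775) + 0.8416·√(0.30·0.70 + 0.15·0.85)]² / 0.15² = 120.5

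With the continuity correction: (120.5/4)·[1 + √(1 + 4/(120.5·0.15))]² = 133.5, so 134 per arm and 268 in total. Then 268/0.8 = 335. Both match. One-sided 5% gives 216, so two-sided 5% is taken as intended.

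**Step 2: size, by approximation.** With four clusters the Wald statistic behaves roughly as t with 3 df. Under a z cut-off:

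- with the G/(G-1) factor: 2·P(t₃ > 1.96) = 14.5%
- without it: 2·P(t₃ > 1.96·√(3/4)) = 18.8%

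**Step 3: power under t(3), by approximation.** The critical value is 3.182. The log odds ratio is ln(0.30/0.70) − ln(0.15/0.85) = 0.887. With m per arm, SE = √(1/(0.21m) + 1/(0.1275m)). At m = 134 the SE is 0.307 and the non-centrality is 2.89. Noncentral t(3) power is 51%, 53% and 57% at N = 268, 288 and 320. The normal reference gives 83%, 85% and 88%.

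**Step 4: simulation.** Assumptions: four sites; logit models with site indicators; site intercept SD 0.4 or 0.8 (logit scale); 3–7 standard-normal baseline covariates with log odds 0.2 each; 15% control rate; 3,000–10,000 replicates per setting (1,500 for the seven heterogeneity tests).

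| Quantity | Clustered, with G/(G-1) | Clustered, without | Model-based |
|---|---|---|---|
| Null rejection, z, equal sites | 14–16% | 19–21% | 5–6% |
| Null rejection, z, unequal sites | 16–19% | 21–24% | – |
| Null rejection, z, continuous outcome | 14% | 19% | 5% |
| 95% CI coverage at 30% vs 15%, z | 85% | 80% | 95% |

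The unequal splits were 120/80/56/32 and 168/60/36/24. Individual-level robust errors also gave 5–6%, and the unadjusted two-proportion test 4–5%. Dropping the site indicators moved the clustered rates by no more than 0.5 points.

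Under t(3) the size is about 5% with equal sites and 6–7% with unequal ones. Power is:

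| Evaluable N | Clustered, t(3) | Model-based | Loss |
|---|---|---|---|
| 268 | 50% | 83% | 33 points |
| 288 | 53% | 86% | 33 points |
| 320 | 57% | 89% | 32 points |

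Separately coded simulations agree. With equal sites they gave 13.5–17% and 18–21% under z, and t(3) power of 49–58% over the same range of N. With no loss to follow-up, t(3) power is 62–64% at 360 and 65–68% at 400.

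**Step 5: the site-by-treatment test.** In a model with site, treatment and their interaction, the score equations force residuals to sum to zero in every site-arm cell. Without covariates each site's score vector is therefore zero, and so is the clustered variance (numerically below 1e-15, against model-based standard errors of 1.3–1.5). With baseline covariates, as planned, only the covariate elements of the scores are non-zero. With 4 covariates the median clustered standard error is 10% of the model-based one (5th–95th percentile 5–20%). The 3-df Wald test then rejects a true null in over 99% of replicates, with a chi-square or an F(3,3) reference. With 7 covariates the figures are 14% and 97–99.7%. A likelihood-ratio test rejects 4–6%.

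**Step 6: the other seven heterogeneity tests.** Clustered z rejects 16–21% each, with at least one false positive in 71–81% of trials. With model-based errors these are 6% and 34%. The 34% is ordinary multiplicity; only the excess comes from clustering.

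**The case against.** The strongest reply is about scope. The trial is powered on, and first tests, an unadjusted difference in proportions. No section makes the adjusted model decisive or promises it 80% power. This stands: the planned power of the primary test is intact.

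Second, the two harms are alternatives, and the plan chooses neither. A t(3) reference does hold size. That is right, but its cost is about 33 percentage points of power, a relative loss of 36–40%.

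Third, Section 10.1 does not say that the interaction is tested by a Wald statistic with the clustered variance; a likelihood-ratio test would also fit the text. That part is therefore conditional. But the variance rule closes the same paragraph and excludes nothing.

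Fourth, if the treatment effect really varies between sites and the target is other sites, fixed-site inference is too liberal. Around a zero average effect it rejects about 7–9% (log-odds SD 0.3) or 13–17% (SD 0.5). At SD 0.5, clustered z with G/(G-1) rejects about 15% and t(3) about 5.6%, so t(3) is the valid choice for that target. This stands as a limit on what the trial can claim.

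Fifth, outcomes may correlate within care coordinator, which site effects do not remove. Assuming two coordinators per site, the model-based test rejects 6–7% (coordinator SD 0.3) or 9.5–10% (SD 0.5). That is a real but smaller inflation than clustered z produces. All these SDs are assumptions.

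**Conclusion.** The concern holds. As written, the variance rule for the adjusted models gives about 14–21% false positives under z with equal sites (up to 24% with unequal ones), or 50–57% power under t(3) at 268–320 evaluable participants. If it is also used for the site-by-treatment test, that test will almost always report heterogeneity, whatever the truth.

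The unadjusted primary test is unaffected. The figures rest on an inferred two-sided 5% level, 20% loss for the power range, and assumed site variation, covariate effects and site sizes. Results changed little across the values of the first two that were tried; unequal sites raised the z-based error and slightly raised t(3) power. If individual-level robust errors were meant, the problem disappears, but the sentence ties them to sites.

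**What to change.** Replace the clustering sentence in Section 10.1 with wording such as:

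> Each adjusted generalised linear model will include site as a fixed effect (three indicators). Standard errors will be model-based or individual-level heteroskedasticity-robust, and will not be clustered on site. Site-by-treatment heterogeneity will be tested with a 3-df likelihood-ratio test. Inference is for the average effect in these four sites.

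Use the same standard errors for the other treatment-by-baseline interactions. Leave the unadjusted primary test as it is.

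Add a rule for site-arm cells with no responders. At a 15% response rate the interaction fit had no finite estimate in about 6% of replicates with equal sites of 72, and in up to 19% in other settings. The likelihood-ratio statistic can still be computed then; the plan should say how site-specific effects will be reported.

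The cost is a few sentences and no new data. Intervals may be wider than the clustered ones, and they will not cover generalisation to other sites, which the report should say.
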